## 15.13. Record Retention

At a minimum, the investigator is responsible for the preparation, review, and retention of the records listed below:

- Essential correspondence that pertains to the investigation
- Records of each subject's case history and exposure to the device. Case histories include the CRFs and supporting data (source documentation), such as:
  - Signed and dated ICFs
  - Medical records, including, for example, progress notes of the physicians, the subject's hospital chart(s) and the nurses' notes
  - All reportable adverse event information
  - Data related to the InterStim Micro System and InterStim Therapy.
- Documentation of any deviation to the protocol, including the date and the rationale for such deviation
- Signed Investigator Agreement and curriculum vitae for all Investigators
- The protocol and any amendments

The Principal Investigator is responsible for ensuring that all essential study documentation is retained and accessible for a minimum of 2 years following completion of the study or according to local regulatory requirements, whichever is greater. The retention period may be longer if required by Medtronic or local or global regulatory requirements; Medtronic will be responsible for notifying sites of extensions to the 2-year minimum record retention requirements. The Principal Investigator will ensure that essential study documents are not destroyed until written permission has been obtained from Medtronic. Medtronic will be notified in writing of any transfer of study documentation. Medtronic will retain the study records according to Medtronic policy.

## 15.14. Publication and Use of Information

Medtronic intends to publish the results from the study in a timely manner upon study completion. These publication activities may include abstracts, presentations/posters to scientific meetings, and manuscripts.

Investigators who gathered data for this study (i.e., enrolled subjects, contributed quality data and complied with the protocol) and are interested in publishing may have the opportunity to write or contribute to the writing of abstracts and manuscripts based on the results of this study. Principal investigators who meet the study-specific criteria above will be considered for abstract/manuscript authorship if they meet the International Committee of Medical Journal Editors, Ethical Considerations in the Conduct and Reporting of Research criteria available via the following link:

<http://www.icmje.org>. Specifically, authorship credit should be based on the following and should meet all criteria listed below:

- Substantial contributions to conception or design; or the acquisition, analysis and interpretation of data for the work;
- Drafting the article or revising it critically for important intellectual content; and
- Final approval of the version to be published; and.
- Agreement to be accountable for all aspects of the work in ensuring that questions related to the accuracy or integrity of any part of the work are appropriately investigated and resolved.

Medtronic employees who meet the International Committee of Medical Journal Editors criteria for authorship will have the right to authorship.

All contributors who do not meet the criteria for authorship are to be listed in an acknowledgment section according to the guidelines of the applicable scientific journal. Examples of those who might be acknowledged include a person who provided purely technical help, writing assistance, or a department chair who provided only general support.

## 15.15. Suspension or Early Termination

Medtronic reserves the right to suspend or terminate the study at any time. Reasons may include, but are not limited to, the following:

- Insufficient enrollment to complete the study within the expected timeframe
- Identification of unacceptable safety profile; suspicion of an unacceptable risk will result in a suspension, confirmation of an unacceptable risk will result in termination
- Inadequate subject adherence to follow-up requirements
- Product performance/product supply issues

Medtronic reserves the right to suspend or terminate the study at an individual site. Reasons may include, but are not limited to, the following:

- Noncompliance with the protocol, including Inadequate subject adherence to follow-up requirements
- Serious or repeated deviations at the site
- Failure to implement required corrective and preventive actions
- Insufficient enrollment to complete the study within the expected timeframe
- Loss of appropriately trained site personnel

Investigators are required to notify the IRB/EC and governing competent authority (if applicable) of study suspension/termination. In addition, Investigators should assess whether or not to continue the study based on reasons above. Subjects will be notified by the investigator of suspension/termination due to unacceptable risk or of termination due to any other cause.

## 17. Appendices

### 17.1 Additional Information for Sites

Detailed sponsor contact information, including the contact information for the local sponsor/legal representative in Europe, Medical Advisor, not outlined in the Clinical Investigational Plan will be provided under a separate cover.

---

#### Medtronic Controlled Information

## 17.2 Institutional Review Boards/Ethics Committees

At the time of the completion of the Clinical Investigation Plan, site selection is not yet complete. Therefore, a complete list of participating IRB/EC names, locations, and the Chairperson(s) will be distributed under a separate cover when available.

## 17.3 Participating Investigators and Institutions

At the time of completion of the Clinical Investigation Plan, site selection is not yet complete. Therefore, a complete list of names, addresses, contact details and professional positions of the clinical investigators and institutions will be distributed under a separate cover when available. No coordinating principal investigator will be assigned for the global portion of the study.

## 17.4 Informed Consent Materials

Copies of all informed consent materials will be provided to the site under a separate cover, based on regional requirements.

## 17.5 Labeling

Copies of the InterStim System Information for Prescribers will be provided to the site under a separate cover, based on regional and local language requirements. All other labeling for commercial products used in the study will be provided through commercial channels.

## 18. Version History

Version	Summary of Changes	Author(s)/Title
1.0	

• 'Not Applicable, New Document'

	[REDACTED] [REDACTED] [REDACTED]
2.0	

• European Legal Sponsor was added to title page

• Study title and purpose was updated to include confirmation of long-term outcomes. Updates based on this change were made throughout the document where applicable.

• Table 11-1: added MPSV (German Safety Plan for Medical Devices) SAE definition

• Section 13.1.1: sample size justification was elaborated to include expected attrition rates and to provide historical rationale for the estimate.

• Section 13.1.3: "All efforts will be made to ensure patient follow-ups are completed with limited

	[REDACTED] [REDACTED]

- |  |  |  |
|--|--|--|
|  | 
attrition to ensure interpretability of study results" was added to the Handling Missing Data paragraph.
 

• Minor grammatical updates throughout

 |  |
|--|--|--|

- Minor grammatical updates throughout

## 1. Version History

Version	Summary of Changes	Author(s)/Title
1.0	Not Applicable, New Document	

## 2. List of Abbreviations and Definitions of Terms

Term	Definition
ADE	Adverse Device Effect
AE	Adverse Event
Basic Evaluation	A temporary test stimulation lead is surgically implanted, externalized and connected to a patient cable for test stimulation.
CCIS	Cleveland Clinic Incontinence Score
CFR	Code of Federal Regulations
CI	Confidence Interval

# ELITE Study Statistical Analysis Plan

Revision 1.0

Page 4 of 24

Form

Medtronic

CIP	Clinical Investigational Plan
CISC	Clean Intermittent Self-Catheterization
DD	Device Deficiency
EU	Europe
FI	Fecal Incontinence
FAS	Full Analysis Set
HRQL	Health Related Quality of Life
OAB-q	Overactive Bladder Symptoms Quality of Life Questionnaire
MI	Multiple Imputation
NOUR	Non-Obstructive Urinary Retention
OAB	Overactive Bladder
PMCF	Post-Market Clinical Follow-up
QoL	Quality of Life
SADE	Serious Adverse Device Effect
SAE	Serious Adverse Event
SAP	Statistical Analysis Plan
SNM	Sacral Neuromodulation
US	United States
UF	Urinary Frequency
UI	Urinary Incontinence
UUI	Urinary Urge Incontinence

### **3. Introduction**

---

This statistical analysis plan (SAP) is based on Clinical Investigational Plan Version 2.0 of the Evaluation of InterStim Micro System Performance and Safety (ELITE) Study. The SAP presents the details of the methods to be used to analyze and report the study results of the ELITE study, protocol number MDT19006.

### **4. Study Objectives**

---

#### **4.1. Overactive Bladder Cohort**

##### **4.1.1. Primary Objective**

The primary objective for the overactive bladder cohort of the study is to demonstrate an improvement in Overactive Bladder Quality of Life (OAB-q) Questionnaire Health Related Quality of Life (HRQL) total score at 3 months post-implant compared to Baseline.

##### **4.1.2. Additional Measures**

- [REDACTED]
- i [REDACTED]
- [REDACTED]
- [REDACTED]
- [REDACTED]
- [REDACTED]

#### **4.2. Fecal Incontinence Cohort**

##### **4.2.1. Primary Objective**

The primary objective for the fecal incontinence cohort of the study is to demonstrate an improvement in Cleveland Clinic Incontinence Score (CCIS) at 3 months post-implant compared to Baseline.

##### **4.2.2. Additional Measures:**

- [REDACTED]
- i [REDACTED]

- [REDACTED]
- [REDACTED]
- [REDACTED]

## 4.3. Non-Obstructive Urinary Retention Cohort

### 4.3.1. Primary Objective

The primary objective for the non-obstructive urinary retention cohort of the study is to demonstrate an improvement in number of clean intermittent self-catheterizations (CISC) per day at 3 months post-implant compared to Baseline.

### 4.3.2. Additional Measures:

- [REDACTED]
- [REDACTED]
- [REDACTED]
- [REDACTED]

## 4.4 Safety Assessment

To characterize safety during the study duration.

To characterize safety of the InterStim Micro System by summarizing the adverse device effects and serious adverse device effects during the study. Safety measures will be summarized for each cohort as well as pooled for all patients regardless of indication. Device deficiencies will also be collected and reported.

Summaries will be presented as number of events, number of subjects who experienced the event, and percent of subjects who experienced the event.

## 5. Investigation Plan

This is a single-arm, prospective, multicenter, open-label, global, post market clinical follow-up for continued assessment of safety and performance of the InterStim Micro System for sacral neuromodulation. The study is intended to be conducted at approximately 40 centers in Australia, Canada, Europe and the United States (including US territories).

[figure not shown]
Subjects will complete Baseline Visit activities after signing a study-specific informed consent form (ICF). Each subject will only be qualified for one of the study cohorts. Once it is confirmed the subject meets eligibility criteria, they will proceed first to an Evaluation Lead Implant Visit and then to a therapy evaluation.

Following the therapy evaluation, once the subject qualifies for the neurostimulator device implant, site personnel may proceed with the Neurostimulator Device Implant Visit. If a subject does not qualify for the neurostimulator device implant, they will be exited from the study. All subjects who met all eligibility criteria and complete the neurostimulator implant procedure will be considered enrolled in the study.

Subjects implanted with the InterStim Micro Neurostimulator will be followed for a total of 2 years with study follow-up visits which should be scheduled within the following targeted visit windows (Table 1), when possible.

**Table 1 Visit windows**

(Target Visit Windows are Calculated from the Date of Neurostimulator Implant)	
Month 3 visit	13 weeks $\pm$ 7 days
Month 6 visit	26 weeks $\pm$ 14 days
Year 1 visit	52 weeks $\pm$ 28 days
Year 2 visit	104 weeks $\pm$ 28 days

**Figure 1 Study visit**

## 6. Determination of Sample Size

For the overactive bladder cohort, the primary objective is to demonstrate an improvement of Overactive Bladder Quality of Life (OAB-q) Questionnaire Health Related Quality of Life (HRQL) score at 3 months post-implant compared to Baseline.

Based on the results of HRQL in OAB-q at 3 months post-implant reported in the InSite study, a mean score change of 30 at 3 months from Baseline with the standard deviation of 27 are the assumptions used for the power calculation for this study. A sample size of 50 achieves greater than 90% power to detect a difference from Baseline of 30 points in OAB-q HRQL total score and a standard deviation of 27 with a significance level of 0.05 using a two-sided one sample t-test.

For the fecal incontinence cohort, the primary objective is to demonstrate an improvement in Cleveland Clinic Incontinence Score (CCIS) at 3 months post-implant compared to Baseline. Based on the result of meta-analysis conducted by Thin et al (2013), a mean CCIS score change of 5 at 3 months from Baseline with the standard deviation of 6.2 are the assumptions used for the power calculation for this study. A sample size of 50 achieves greater than 90% power to detect a difference from Baseline of 5 points in Cleveland Clinic Incontinence Score (CCIS) and a standard deviation of 6 with a significance level of 0.05 using a two-sided one sample t-test.

For the non-obstructive urinary retention cohort, the primary objective is to demonstrate an improvement in number of clean intermittent self-catheterizations (CISC) per day at 3 months post-implant compared to Baseline. Based on the literature results published in Van Kerrebroeck et al (2007), Sutherland et al (2007), Cardarelli et al (2012) and MDT-103 and SOUNDS interim reports, a mean change of 2 in the number of CISC/day between Baseline and 3 months post-implant ( $\mu$ ) with a standard deviation of 3 are the assumptions used for the power calculation for this study. A sample size of 30 achieves greater than 90% power to detect a difference from Baseline of 2 CISC/day and a standard deviation of 3 with a significance level of 0.05 using a two-sided one sample t-test.

The power calculations were performed using PASS 11 statistical software for all three cohorts. To accommodate attritions, approximately 160 subjects (60 for overactive bladder cohort, 60 for fecal incontinence cohort and 40 for non-obstructive urinary retention cohort), will be enrolled in the study to achieve a minimum of 50 evaluable subjects each for overactive bladder and fecal incontinence cohorts and a minimum of 30 evaluable implanted subjects for non-obstructive urinary retention cohort at 3 months post implant.

## **7. Statistical Methods**

---

### **7.1 Study Subjects**

#### **7.1.1 Disposition of Subjects**

For all the three cohorts separately, subject disposition will be summarized by study visit in a flow diagram. Discontinuation will be summarized by visit and discontinuation reasons will be provided.

#### **7.1.2 Clinical Investigation Plan (CIP) Deviations**

For all the three cohorts separately, all CIP deviations will be summarized by type of deviation. Details of CIP deviations that affect scientific integrity or patient safety may be presented.

#### **7.1.3 Analysis Sets**

- The **Consented Subject Set** includes all subjects who signed the study-specific informed consent form (ICF).
- The **Test Subject Set** includes all subjects who underwent a lead placement attempt, whether the procedure was successful or not.
- The **Full Analysis Subject Set (FAS)** includes all subjects who signed the study-specific ICF and enrolled in the study. Subjects are considered enrolled at completion of the neurostimulator implant procedure.

- The **Complete Case Subject Set (CC)** consist of the subjects implanted with the Neurostimulator Device (Enrolled) and who have data available at Baseline and at each follow up visit.

## 7.2 General Methodology

This is a non-randomized study to explore efficacy, safety, and quality of life (QoL) with sacral neuromodulation on three independent cohorts (OAB, FI, NOUR). The statistical analysis will be held for each cohort separately and independently, but some general methodologies will be used in all cohorts.

Continuous measures will be reported as N, means, medians, standard deviations, minimums and maximums. Categorical measures will be reported in frequency distributions. Summaries will be completed for all subjects (pooled).

For outcomes examining change from Baseline, change ( $\Delta$ ) will be calculated as follow-up scores ( $S_v$ ) minus Baseline scores ( $S_0$ ).

$$\Delta = S_v - S_0$$

Percentage change will be calculated as 100 times the change divided by the Baseline score.

$$\text{Percentage change} = 100 * \Delta / S_0$$

95% Confidence intervals may be also derived as follow

$$\bar{x} \pm z * \frac{\sigma}{\sqrt{n}}$$

Where  $\bar{x}$  is the sample mean,  $z$  is the z-value from the standard normal distribution for the 95% confidence level,  $\sigma$  is the sample standard deviation and  $n$  is the sample size.

Data analysis will be performed by Medtronic-employed statisticians or designees. A validated statistical software package (e.g., SAS version 9.4 or higher) will be used to analyze the study results.

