  - ModelEffects = mean change in OAB-q HRQL (OAB cohort) OR CCIS (FI cohort) OR number of CISC (NOUR cohort)
  - StdErr = standard error of change in OAB-q HRQL (OAB cohort) OR CCIS (FI cohort) OR number of CISC (NOUR cohort)

The output ParameterEstimates dataset from the MI analysis will contain the adjusted estimate of the mean and standard error of change in OAB-q HRQL (OAB cohort) OR CCIS (FI cohort) OR number of CISC (NOUR cohort), the 95% confidence interval for the mean change, and the associated t-statistic and p-value from the test of the null hypothesis.

- If normality assumption is not met, the fully conditional method (FCS) with Predictive mean matching (PMM) is chosen to perform multiple imputation for continuous variables (primary objective effectiveness). The Predictive mean matching (PMM) model is implicit (Little and Rubin 2002), which means that there is no need to define an explicit model for the distribution of the missing values. Because of this, predictive mean matching is less vulnerable to model misspecification than the regression methods. The fully conditional method (FCS) does not assume a joint distribution but instead uses a separate conditional distribution for each imputed variable, and FCS method does not require a monotone missing data pattern. The combination of FCS with PMM method is selected due to these reasons. SAS MI procedure will be used with SEED=13951639 and number of imputations=30. After MI procedure, m (m=30) imputed data are obtained. The resulting distribution is likely to be skewed, therefore median will be used to summarize the m imputed datasets instead of mean. The standard error of median calculated from each imputed dataset will be estimated through bootstrap method. Then MIANALYZE procedure is used to combine the results.

The model variables in the MI analysis in both cases (normality and non normality) may include:

- For OAB cohort:
  - Age

- Gender
- Baseline OABq HRQL
- Baseline UUI episodes
- Baseline voids
- Secondary OAB diagnosis: Stress incontinence, Urinary frequency, retention, pelvic pain, interstitial cystitis, or none
- Medical history
- The number of ongoing OAB medications used at baseline
- Motor response at tined lead implant
- For FI cohort:
  - Age
  - Gender
  - Baseline CCIS
  - Baseline movements
  - Baseline accidents
  - Medical history
  - Motor response at tined lead implant
  -
- For NOUR cohort:
  - Age
  - Gender
  - Baseline number of catheterizations

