#### 7.9.1.4 Analysis Methods and Presentation Format

In case the normality assumption of data will hold (Shapiro Will test), a two-sided one sample t-test will be performed to test the hypothesis described in section 7.9.1.2.

In case the normality assumption of data will not hold (Shapiro Will test), a Wilcoxon Singed Rank test will be performed to test the hypothesis described in section 7.9.1.2.

In addition to the hypothesis testing, the two-sided 95% confidence interval for the mean change in HRQL total score will be calculated and reported.

In cases where subject's OAB-q HRQL total score is missing at Baseline and/or at 3 months post-implant for any reasons, the percentage of missing data will be summarized and a sensitivity analysis using multiple imputation will be performed as described in section 7.4.

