#### 7.9.2.4 Analysis Methods and Presentation Format

In case the normality assumption of data will hold (Shapiro Will test), a two-sided one sample t-test will be performed to test the hypothesis described in section 7.9.1.2.

In case the normality assumption of data will not hold (Shapiro Will test), a Wilcoxon Singed Rank test will be performed to test the hypothesis described in section 7.9.1.2.

In addition to the hypothesis testing, the two-sided 95% confidence interval for the mean change in CCIS will be calculated and reported.

In cases where subject's CCIS is missing at Baseline and/or at 3 months post-implant for any reasons, the percentage of missing data will be summarized and a sensitivity analysis using multiple imputation will be performed as described in section 7.4.

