#### 7.9.3.2 Hypothesis

The null ( $H_0$ ) and alternative ( $H_1$ ) hypotheses are:

$$H_0: \mu = 0$$

$$H_a: \mu \neq 0$$

Where  $\mu$  indicates the mean change in the number of CISC per day from Baseline to 3 months post-implant. P-value will be evaluated at alpha level of 0.05.

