#### 7.9.3.4 Analysis Methods and Presentation Format

In case the normality assumption of data will hold (Shapiro Will test), a two-sided one sample t-test will be performed to test the hypothesis described in section 7.9.3.2.

In case the normality assumption of data will not hold (Shapiro Will test), a Wilcoxon Singed Rank test will be performed to test the hypothesis described in section 7.9.3.2.

In addition to the hypothesis testing, the two-sided 95% confidence interval for the mean change in number of CISC will be calculated and reported.

In cases where subject's number of CISC per day is missing at Baseline and/or at 3 months post-implant for any reasons, the percentage of missing data will be summarized and a sensitivity analysis using multiple imputation will be performed as described in section 7.4.

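### The only legible confidence-interval formula in the SAP uses the normal z with an estimated SD; applied to the primary outcomes it would give intervals 2.5% to 4.2% too narrow at the minimum sample sizes

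*SAP*

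**What the plan says.** SAP section 7.2 (General Methodology) introduces its interval permissively: "95% Confidence intervals may be also derived as follow". The formula is the sample mean ± z × σ/√n. The multiplier z "is the z-value from the standard normal distribution for the 95% confidence level", and σ is defined as the standard deviation of the sample, not a known population value.

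The primary-analysis sections make an interval mandatory in each cohort:

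- OAB (7.9.1.4): "the two-sided 95% confidence interval for the mean change in HRQL total score will be calculated and reported"
- FI (7.9.2.4): "the two-sided 95% confidence interval for the mean change in CCIS will be calculated and reported"
- NOUR (7.9.3.4): "the two-sided 95% confidence interval for the mean change in number of CISC will be calculated and reported"

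None of the three gives a formula or refers back to 7.2. The matching protocol sections (13.4.1, 13.5.1, 13.6.1) also require the interval without a formula.

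The test in the same sections is t-based when the Shapiro-Wilk check supports normality. For NOUR, "a two-sided one sample t-test will be performed to test the hypothesis described in section 7.9.3.2", with "P-value will be evaluated at alpha level of 0.05" (7.9.3.2). Otherwise a Wilcoxon signed rank test is used. In section 7.4, the normal branch of the multiple-imputation sensitivity analysis sets the degrees of freedom to a sample size minus 1 and reports "the 95% confidence interval for the mean change, and the associated t-statistic and p-value from the test of the null hypothesis".

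**The concern.** The normal multiplier is exact only when the SD is known. Here it is estimated from 30 to 60 subjects, so under normality the standardised mean follows a t distribution on n−1 degrees of freedom, and 1.960 is too small.

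A programmer who looks in the SAP for the method behind the required primary interval finds one formula, and it is the z version. The complete-case interval could then be z-based while the test of the same mean change, and the multiple-imputation interval for it, are t-based. The reported interval would cover slightly less than its stated 95%. In a narrow band of results it would exclude zero although the t-test does not reject.

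**Working it through.** **Inputs.** Minimum evaluable numbers are 50 (OAB), 50 (FI) and 30 (NOUR), from SAP section 6. Planning values from the same section are a mean change of 30 with SD 27 (OAB), 5 with SD 6.2 (FI; a later sentence uses SD 6) and 2 with SD 3 (NOUR). Two-sided alpha is 0.05. Protocol 13.1.1 plans 60, 60 and 40 implants with attrition below 10% by 3 months. At 10% attrition that leaves 60 × 0.9 = 54 and 40 × 0.9 = 36.

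**The plan's own figure first.** The documents state no interval width or coverage. They do state power above 90%. With noncentrality (mean/SD) × √n, the exact two-sided one-sample t-test gives:

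- OAB: 30/27 × √50 = 7.86, power above 99.99%
- FI: 5/6.2 × √50 = 5.70, power 99.99% (also 99.99% at SD 6)
- NOUR: 2/3 × √30 = 3.65, power 94.2%

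The stated power is reproduced in all three cohorts.

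**Width and coverage of the z interval.** With z = 1.95996 and t = t(0.975, n−1):

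- narrowing = 1 − z/t
- coverage under normality = 1 − 2 × P(T with n−1 df > z)

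| n | t | Narrowing | Coverage |
|---|---|---|---|
| 30 (NOUR minimum) | 2.0452 | 4.17% | 94.03% |
| 36 (NOUR, 10% attrition) | 2.0301 | 3.46% | 94.20% |
| 40 (NOUR, none lost) | 2.0227 | 3.10% | 94.28% |
| 50 (OAB, FI minimum) | 2.0096 | 2.47% | 94.43% |
| 54 (OAB, FI, 10% attrition) | 2.0057 | 2.28% | 94.47% |
| 60 (OAB, FI, none lost) | 2.0010 | 2.05% | 94.53% |

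For example, at n = 30: 1 − 1.95996/2.0452 = 0.0417. The percentages do not depend on the SD.

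**Half-widths at the planning SDs** (multiplier × SD/√n):

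| Cohort | SD/√n | With z | With t |
|---|---|---|---|
| NOUR, CISC/day | 3/√30 = 0.5477 | 1.074 | 1.120 |
| FI, CCIS points, SD 6.2 | 6.2/√50 = 0.8768 | 1.719 | 1.762 |
| FI, CCIS points, SD 6 | 6/√50 = 0.8485 | 1.663 | 1.705 |
| OAB, HRQL points | 27/√50 = 3.8184 | 7.484 | 7.673 |

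**Chance that interval and t-test disagree.** This happens when z < |T| < t. At n = 30 the band is 1.960 < |T| < 2.045, which corresponds to p between 0.050 and 0.060.

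- Under the null the probability is 0.95 minus the coverage: 0.97% at n = 30 and 0.57% at n = 50.
- At the planned effect (noncentral t) it is 0.94% for NOUR at n = 30, 0.41% for NOUR at n = 36, and below 0.003% for FI and OAB at n = 50.

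**The case against.** The strongest reply is that nothing ties this formula to the primary intervals. It is permissive, it sits among general descriptive methods, and the primary sections do not cite 7.2 although they cite other sections where needed. It may have been meant for the additional measures, whose sections are redacted. The one primary-outcome interval described in any detail, in the normal branch of 7.4, is t-based, which suggests the authors intend t throughout. That is a fair reading, and it is why the finding is conditional. It does not remove the problem: the primary intervals are mandatory, their method is not stated, and the only written formula gives the wrong multiplier.

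A second reply is that the effect is small and the quoted range is the worst case. This stands. With attrition at or below 10% the narrowing is at most 3.5% (NOUR) and 2.3% (OAB, FI), and z is a familiar large-sample approximation. The hypothesis is judged by the p-value, so no decision changes.

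A third reply is that the mismatch with the test exists only in the normal branch. This also stands. If the Wilcoxon test is used, neither a z nor a t interval for the mean corresponds to it.

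Finally, SAP section 8 requires independent programming of the primary output, so a z-versus-t discrepancy could be caught. That works only if the two programmers choose differently, and the SAP would still not say which of them is right.

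**Conclusion.** The concern holds, as a minor point. SAP 7.2 pairs a normal multiplier with an estimated SD, and no other legible formula serves the required primary intervals. If it is used, the intervals are 4.2% too narrow for NOUR at n = 30 and 2.5% too narrow for OAB and FI at n = 50, with coverage of 94.0% and 94.4% instead of 95%. The largest chance of disagreement with the t-test is just under 1%, in NOUR at the minimum sample size.

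These figures assume normally distributed changes and that z is in fact applied to the primary outcomes. The half-widths and the planned-effect probabilities also assume the planning values. The primary test, its type I error, the power and the sample size are not affected; only the reported interval is.

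**What to change.** In SAP 7.2, replace z with t(0.975, n−1) and write s instead of σ for the sample SD. In 7.9.1.4, 7.9.2.4 and 7.9.3.4, state that the primary interval for the mean change is the one-sample t interval. Add a sentence that when the Wilcoxon test is used, the interval for the mean is descriptive and may not agree with that test.

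The cost is a few lines of SAP text and no new data. Relative to the z version the intervals widen by t/z − 1: 2.5% at n = 50 (2.0096/1.95996) and 4.4% at n = 30 (2.0452/1.95996, 4.35% before rounding). The change does not make the interval agree with the Wilcoxon test in the non-normal branch, which is why the added sentence is needed.
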